4. CHANGES IN THE PLANNED ANALYSIS OF THE STUDY

Descriptive statistics for primary and secondary endpoints will be based on the MCS rather than TS to be consistent with the model-based analyses.

There are no further changes in the planned analysis of the study.

5. ENDPOINTS

Figure 5.1:1 in the CTP displays all spirometry measurements during one treatment period that is during the baseline bolus challenge prior to drug administration, during drug administration and during the treatment challenge on Day 2.

In the following baseline refers to the measurement obtained from the baseline bolus Methacholine (MCh) challenge prior to administration of trial medication within each period.

5.1 PRIMARY ENDPOINT

CTP: *The primary endpoint for the study to assess safety of BI 443651 is*

- *Absolute change from baseline in maximum FEV₁ reduction following MCh challenge*

The primary endpoint will be compared to placebo for each dose level of BI 443651.

For a visualization of the endpoint refer to Figure 5.1:1, a detailed description of the primary endpoint and the primary statistical analysis is provided in Section 7 of the CTP.

5.2 SECONDARY ENDPOINTS

CTP: *The following secondary endpoints will be assessed:*

- *Relative change from baseline in FEV₁ AUC_{0-tz} following bolus MCh challenge*
- *Time to recovery of FEV₁ to within 95% of post-diluent value*

The secondary endpoints will be compared to placebo for each dose level of BI 443651.

For a visualization of the endpoints refer to Figure 5.1:1, a detailed description of the secondary endpoints including statistical analysis is provided in Section 7 of the CTP.

6. GENERAL ANALYSIS DEFINITIONS

6.1 TREATMENT(S)

For basic study information on treatments to be administered please refer to Section 4 of the CTP.

The trial is composed of two parts: The first part (pilot study) will be a single-blind four-way crossover with dose ordered sequences. The second part (main study) will be a double-blind four-way crossover, conducted according to a William's design. In both parts of the study, BI 443651 or placebo equivalent will be administered three consecutive times, 12 hours apart, per dose level. All subjects will receive placebo, 100, 400 and 1200 µg BI 443651. Each period will be separated by a washout period of at least 14 days (and not more than 28 days). Two administrations of BI 443651 will be delivered on Day 1 (morning and evening) and a single administration on Day 2 (morning).

Table 6.1: 1 Treatments and labels used in the analysis (for both trial parts)

Treatment		Short label
P	Placebo, respimat, bid	Plc
A	BI 443651 Respimat, 1*100 mcg/actuation, ih, bid	BI 100
B	BI 443651 Respimat, 4*100 mcg/actuation, ih, bid	BI 400
C	BI 443651 Respimat, 4*300 mcg/actuation, ih, bid	BI 1200

Table 6.1: 2 Overview of treatments for intra-individual comparison

Test treatment (T)		Reference treatment (R)	
BI 100	(A)	Placebo	(P)
BI 400	(B)	Placebo	(P)
BI 1200	(C)	Placebo	(P)

Measurements (such as ECG, vital signs, or laboratory parameters) or adverse events (AE) will be assigned to treatments and study periods by applying the following rules:

- **Screening:** measurements planned or AEs recorded prior to first device actuation for administration of trial medication.
- **On-treatment:** measurements planned or AEs recorded between first device actuation for administration in one treatment period until first device actuation for administration of trial medication in the next treatment period or until the end of the respective residual effect period (REP) or until trial completion date (whichever occurs first) will be assigned to the preceding treatment. The REP for BI 443651 is defined as after the last trial medication application.

- **Follow-up:** measurements planned or AEs recorded between the end of REP of one treatment period and the first device actuation for treatment administration of the next treatment period or trial completion date. In case of more treatments, the follow-up will be summarized according to the previous treatment.

Table 6.1: 3 Flow chart of analysis phases for adverse events, laboratory tests, vital signs and spirometry

Study analysis phase	Start	End
Screening	Date of informed consent	Date/time of first device actuation for administration of BI 443651 or placebo (first period)
On treatment	Date/time of first device actuation for administration of BI 443651 or placebo (in the actual treatment period)	0:00 AM on day after end of REP or trial completion date or date/time of first device actuation for drug administration in the next treatment period
Follow-up	0:00 AM on day after end of REP	trial completion date or date/time of first device actuation for drug administration in the next treatment period

6.2 IMPORTANT PROTOCOL VIOLATIONS

Data discrepancies and deviations from the CTP will be identified for all subjects in the database (i.e. for all randomised subjects). Consistency check listings (for identification of violations of time windows) and a list of protocol deviations (e.g. deviations in drug administration, in blood sampling times, etc.) will be provided to be discussed at the blinded report planning and database lock meeting (BRPM/DBLM). At this meeting, it will be decided whether a discrepant data value can be used in analyses or whether it must be corrected in the clinical database. Each protocol deviation must be assessed to determine whether it is an important protocol violation (PV). For definition of important PVs, and for the process of identification of these, refer to the Boehringer Ingelheim (BI) reference document "Protocol Violation Handling Definitions" (7).

If any important PVs are identified, they are to be summarised into categories and will be captured in the BRPM/DBLM minutes via an accompanying Excel spreadsheet (8). The following Table 6.2: 1 contains the categories which are considered to be important PVs in this trial. The last column describes which iPVs will be used to exclude subjects from the different subject analysis sets by default. The final decision about exclusion from analysis sets will be made at the BRPM/DBLM. If the data show other important PVs, this table will be supplemented accordingly by the time of the BRPM/DBLM.

IPVs will be summarised and listed.

Table 6.2: 1 Important protocol violations

Category / Code	Description	Example/Comment	Excluded from
A	Entrance criteria not met		
A1	Inclusion criteria violated*	Decision at BRPM/DBLM	None
A2	Exclusion criteria violated*	Decision at BRPM/DBLM	None
B	Informed consent		
B1	Informed consent not available*	Informed consent date missing; no signature on ICF	All
B2	Informed consent too late*	Date of informed consent was after the date of any study-related procedure, or a patient signed the correct version of the ICF after Visit 1. To be discussed at BRPM/DBLM.	None
C	Trial medication and randomisation		
C1	Incorrect trial medication taken*	Decision at BRPM/DBLM	None
C2	Randomisation order not followed*		None
C3	Non-compliance*	Decisions at BRPM/DBLM	None
C4	Medication code broken inappropriately*	To be discussed and decided during BRPM/DBLM. Only inappropriate code breaks at IPVs (e.g., unblinding by Global Pharmacovigilance is not).	None
C5	Incorrect intake of trial medication*	Decision at BRPM/DBLM	None
C6	Improper washout between treatments*	Decision at BRPM/DBLM	None
D	Concomitant medication		
D1	Prohibited medication use*	Decision at BRPM/DBLM	None
D2	Mandatory medication not taken*	Decision at BRPM/DBLM	None
D3	Improper washout of concomitant medication*	Decision at BRPM/DBLM	None
E	Missing data		
E1	Certain violations of procedures used to measure primary or secondary data*	Decision at BRPM/DBLM	None
F	Incorrect timing		
F1	Certain violations of time schedule used to measure primary or secondary data*	Decision at BRPM/DBLM	None

KEY: * not programmed

6.3 SUBJECT SETS ANALYSED

CTP: *The statistical analysis will be based on the following analysis sets based on the actual treatment the subject receives.*

- *Enrolled set (ES): This subject set includes subjects that signed informed consent and underwent screening procedures.*
- *Randomised set (RS): This subject set includes all randomised subjects, whether treated or not.*
- *Treated set (TS): The treated set includes all subjects who were randomised and treated with at least one dose of study drug. The treatment assignment will be determined based on the first treatment the subjects received.*
- *Methacholine set (MCS): This subject set includes all subjects in the treated set who provide at least one pair (baseline and end of treatment) of evaluable measures of spirometry parameters that were not excluded due to use of rescue medication within 3 hours after start of MCh challenge.*

Table 6.3: 1 Subject sets analysed

Class of endpoint	Subject set			
	ES	RS	TS	MCS
Disposition	X			
Exposure			X	
Important PVs		X		
Demographic data /baseline conditions			X	(X)*
Primary and secondary endpoints				
• Descriptive statistics				X
• Mixed effects model				X
Further safety parameters			X	

* An additional MCS presentation of the demographic/baseline endpoints may be provided in the EoT section, if subject numbers for MCS and treated set are clearly different.

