7.3.1 Primary endpoint analyses

The primary endpoint absolute change from baseline in maximum reduction in FEV₁ (refer to [Section 5.1.1](#)) is defined as the difference between the maximum reduction in FEV₁ obtained during the treatment challenge and during the baseline challenge.

The primary endpoint will be investigated using descriptive statistics for both trial parts separately and combined.

For the main part of the trial (part II), this primary endpoint will be analysed using a mixed effects model based on the MCS:

$$y_{imj} = \mu + \pi_m + \tau_j + \gamma b_{im} + \gamma' b'_i + s_i + e_{imj},$$

where i = subject 1,..., N, m = period 1,...,4, j = treatment 1,...,4

y_{imj}	CfB in maximum FEV ₁ reduction for the i th subject and the m th period, receiving randomised treatment j
μ	overall intercept,
π_m	m th period effect,
τ_j	j th treatment effect,
b_{im}	baseline value for subject i in period m (period baseline),
γ	associated covariate effect of period baseline,
b'_i	the subject baseline value (mean of period baselines) for subject i,
γ'	associated covariate effect of subject baseline,
s_i	the random effect of subject i,
e_{imj}	the random error associated with subject i who received treatment j in period m.

Proprietary confidential information © 2017 Boehringer Ingelheim International GmbH or one or more of its affiliated companies

The treatment comparisons will be the contrast between active dose and placebo at the endpoint visit. Adjusted means (Least Squares Means) as well as 2-sided 90% Cis will be provided.

Further details will be provided in the TSAP.

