7.3.5 Safety analyses

Safety will be assessed for the further safety parameters of interest listed in [Section 5.1.3](#) based on the TS. Safety analyses will be descriptive in nature and will be based on BI standards.

Treatments will be compared in a descriptive way. The active treatment groups will be compared to the placebo group in a descriptive way. Tabulations of frequencies/proportions will be used for the evaluation of categorical (qualitative) data, and tabulations of descriptive statistics will be used to analyse continuous (quantitative) data.

The analyses will be done by ‘treatment at onset’.

Measurements (such as ECG, vital signs, or laboratory parameters) or Aes will be assigned to treatments (see [Section 4.1](#)) based on the actual treatment at the planned time of the measurement or on the recorded time of AE onset (concept of treatment emergent Aes).

Therefore, measurements planned or Aes recorded prior to first intake of trial medication will be assigned to ‘screening’, those between first trial medication intake until next intake or end of REP will be assigned to the preceding treatment, and all Aes occurring between the end of REP and next treatment intake or trial termination date respectively will be assigned to ‘follow-up’. In case of two or more treatments, the follow-up will be summarized according to the previous treatment. These assignments including the corresponding time intervals will be defined in detail in the TSAP. Please note that Aes occurring after the last per protocol contact but entered before database lock will be reported to drug safety only and will not be captured in the trial database.

Additionally, further treatment intervals (analysing treatments) may be defined in order to provide summary statistics for time intervals, such as combined treatments, on-treatment totals or periods without treatment effects (such as screening and follow-up intervals).

Adverse events will be coded using the Medical Dictionary for Regulatory Activities (MedDRA). Frequency, intensity and causal relationship of Aes will be tabulated by treatment, primary system organ class and preferred term. SAEs, AESIs ([see Section 5.3.6](#)) and other significant Aes (according to ICH E3) will be listed separately.

Laboratory data will be compared to their reference ranges. Values outside the reference range will be flagged. Additionally, differences from baseline will be evaluated.

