7. PLANNED ANALYSIS

The format of the listings and tables will follow the BI guideline "Reporting of clinical trials and project summaries" ([9](#)).

The individual values of all subjects will be listed, sorted by treatment sequence, subject number and visit (if visit is applicable in the respective listing). AE listings will be sorted by assigned treatment (see Section [7.8.1](#) below for details). The listings will be contained in Appendix 16.2 (SDL) of the CTR.

The following standard descriptive statistical parameters will be displayed in summary tables of continuous variables:

N	number of non-missing observations
Mean	arithmetic mean
SD	standard deviation
Min	minimum
Median	median
Max	maximum

For endpoints related to MCh challenge, the set of summary statistics is: N / Mean / SD / Min / Q1 (1st quartile) / Median / Q3 (3rd quartile) / Max.

Tabulations of frequencies for categorical data will include all possible categories and will display the number of observations in a category as well as the percentage (%) relative to the respective treatment group. Percentages will be rounded to one decimal place. The category missing will be displayed only if there are actually missing values. Percentages will be based on all subjects in the respective analysis set whether they have non-missing values or not.

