7.8 SAFETY ANALYSIS

All safety analyses of further safety parameters of interest will be performed on the treated set (and will be presented for both trial parts combined).

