7.8.1 Adverse events

AEs will be coded with the most recent version of MedDRA.

The analyses of AEs will be descriptive in nature. All analyses of AEs will be based on the number of subjects with AEs and not on the number of AEs.

For analysis, multiple AE occurrence data on the electronic case report form (eCRF) will be collapsed into one event provided that all of the following applies:

- All AE attributes are identical (lower level term, intensity, action taken, therapy required, seriousness, reason for seriousness, relationship, outcome, AE of special interest (AESI))
- The occurrences were time-overlapping or time-adjacent (time-adjacency of two occurrences is given if the second occurrence started at most 1 hour after the first occurrence ended)

For further details on summarization of AE data, please refer to 'Handling and summarization of adverse event data for clinical trial reports and integrated summaries' ([4](#)) and "Handling of missing and incomplete AE dates" ([3](#)).

The analysis of AEs will be based on the concept of treatment emergent AEs, i.e. all AEs will be assigned to the treatment phase, screening phase or follow-up phase as defined in Section [6.1](#).

An overall summary of AEs will be presented. This overall summary will comprise summary statistics for the class of other significant AEs according to ICH E3 and for the class of adverse events of special interest (AESI). For the definition of AESI please refer to Section 5.3.6.1 of the CTP.

The frequency of subjects with AEs will be summarised by treatment, primary system organ class and preferred term. AEs which were considered by the investigator to be drug related will be summarised separately. Separate tables will also be provided for subjects with serious AEs (SAEs), related SAEs, subjects with AESIs and subjects with other significant AEs (according to ICH E3 ([5](#))). AEs will also be summarized by maximum intensity.

The system organ classes will be sorted according to the standard sort order specified by the European Medicines Agency (EMA), preferred terms will be sorted by total frequency (within system organ class).

For disclosure of AE data on ClinicalTrials.gov, the frequency of subjects with non-serious AEs occurring with an incidence of greater than 5 % (in preferred terms) will be summarised by treatment, primary system organ class and preferred term. The frequency of subjects with SAEs will also be summarised.

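### The treated-set definition assigns each crossover subject to the first treatment received, and nothing else in the plan sets the right per-treatment denominator for the further-safety tables

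*SAP*

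**What the plan says.** **Analysis set.** The lead-in in SAP 6.3 reads "The statistical analysis will be based on the following analysis sets based on the actual treatment the subject receives". The treated-set entry under it then adds "The treatment assignment will be determined based on the first treatment the subjects received". Protocol 7.3 has the same text, and the SAP reproduces it as protocol text. SAP section 4 lists one change from the protocol (endpoint descriptive statistics move to the methacholine set) and does not touch this sentence.

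**Use of the set.** SAP 7.8: "All safety analyses of further safety parameters of interest will be performed on the treated set", with both trial parts combined. Primary and secondary endpoints use the methacholine set instead (SAP 6.3, 7.4, 7.5).

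**Placing events and measurements.** Protocol 7.3.5 assigns them "based on the actual treatment at the planned time of the measurement or on the recorded time of AE onset". SAP 6.1 gives the same period-wise rule: data from the first actuation in one period to the first actuation in the next, or to the end of the residual effect period, "or until trial completion date (whichever occurs first) will be assigned to the preceding treatment". SAP 7.8.1 applies this to adverse events: "all AEs will be assigned to the treatment phase, screening phase or follow-up phase as defined in Section" 6.1.

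**Percentages.** SAP 7 makes percentages relative to the treatment group, a term it does not define for a crossover. It then says "Percentages will be based on all subjects in the respective analysis set whether they have non-missing values or not".

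**The concern.** Adverse events are tabulated as subjects with an event, not as event counts (SAP 7.8.1), so every percentage needs a number of subjects per treatment. The period-wise rules decide which treatment an event belongs to. They do not say how many subjects that treatment has. SAP 7.7 plans exposure only as a listing, so it does not supply the count either.

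Two texts bear on it. One is the first-treatment sentence, the only rule that attaches treated-set subjects, as distinct from events or measurements, to a treatment. The other is the percentage sentence in SAP 7. Neither, taken as written, gives the number of subjects exposed to the treatment in question. Adverse-event and laboratory percentages by dose depend on that number, and they support the trial's stated objective of safety and tolerability at three dose levels.

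**Working it through.** The plan gives no column sizes for its safety tables, so only the planned total can be reproduced: 4 (Part 1) + 32 (Part 2) = 36, as in the protocol synopsis.

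**Step 1. Subjects per treatment under each rule.**

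Inputs:
- Protocol Table 3.1:1: the four Part 1 sequences start with placebo, 100, 100 and 100 µg. Four subjects are allocated 1:1:1:1 (protocol 7.6), so one per sequence.
- Protocol Table 3.1:2: the four Part 2 sequences start with placebo, 100, 400 and 1200 µg, with 8 subjects per sequence (protocol 7.7).
- Assumption: all 36 complete, with no replacements and no added dose levels in Part 1.

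| | Placebo | 100 µg | 400 µg | 1200 µg |
|---|---|---|---|---|
| First treatment, Part 1 | 1 | 3 | 0 | 0 |
| First treatment, Part 2 | 8 | 8 | 8 | 8 |
| First treatment, both parts | 9 | 11 | 8 | 8 |
| Exposed to the treatment | 36 | 36 | 36 | 36 |
| Inflation of a percentage, 36/n | 4.0 | 3.3 | 4.5 | 4.5 |

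The first-treatment denominators are too small, and unequally so. Six subjects with an event on each treatment should read 6/36 = 16.7% throughout. They would read 6/9 = 66.7%, 6/11 = 54.5%, 6/8 = 75.0% and 6/8 = 75.0%.

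**Step 2. All subjects in the set as denominator.** Let x be subjects with an event on a dose, E those exposed to it, and k treated-set subjects who never received it. The correct percentage is x/E; the SAP 7 sentence, read literally, gives x/(E + k).

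A positive k follows from the design whenever someone withdraws before a dose and is replaced (protocol 3.3.5): the treated set grows past 36 while the number reaching that dose stays at 36. In Part 1 the 1200 µg dose comes only in period 3 or 4, so an early withdrawal removes exposure to it, and the replacement takes only the missed periods. The documents do not give k, so a range is shown with x = 6 and E = 36 (x also assumed):

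| k | x/(E + k) | Result |
|---|---|---|
| 0 | 6/36 | 16.7% |
| 2 | 6/38 | 15.8% |
| 4 | 6/40 | 15.0% |
| 8 | 6/44 | 13.6% |

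**Step 3. Can so small a shift matter?** SAP 7.8.1 keeps non-serious events above 5% incidence for the registry tables. If that threshold is applied per treatment, which the SAP does not say, two subjects with an event give 2/36 = 5.6% (kept) or 2/40 = 5.0% (not kept).

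**The case against.** **A reader might infer that the safety tables will have wrong columns.** If the first-treatment sentence governed placement, 36 × 3 = 108 of 36 × 4 = 144 subject-periods (75%) would sit under a treatment not given in that period. The documents do not support this. Protocol 7.3.5 and SAP 6.1 and 7.8.1 are specific and consistent, and they place events and measurements under the treatment actually taken.

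**A reader might take 6/8 = 75% as a planned result.** It is not. It combines a treatment-at-onset numerator with a first-treatment denominator, and no text prescribes that combination. It could also exceed 100% (nine subjects with events over eight), so a draft table would probably expose it. It shows the literal extreme only.

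**A reader might extend the point to the main comparisons.** The models run on the methacholine set with a treatment term per period, so the sentence does not reach them. Their definition does say "receiving randomised treatment j" where the set lead-in says actual treatment. The two differ only after a dosing error, which SAP 6.2 sends to the blinded meeting. Nor does the treated set carry all safety results: the primary endpoint is itself a safety endpoint and uses the other set.

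**The SAP 7 sentence may be only about missing values.** Its closing clause suggests so, and the preceding text ties percentages to the treatment group. That is a fair reading and probably the intended one. But the sentence names the whole analysis set as the base, and the treatment group is undefined, so the text does not exclude never-exposed subjects.

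**The convention may be in a sponsor standard.** SAP 7.8.1 and 7.8.2 refer to internal standards for adverse-event and laboratory tables, and these may define the denominator. This lowers the chance of an actual error. It does not remove a contrary trial-specific sentence from both documents.

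**Conclusion.** The point holds for denominators only. The first-treatment sentence is wrong for a four-way crossover, conflicts with its own lead-in and with the period-wise rules, and is left standing by SAP section 4. Followed literally, it gives 9/11/8/8 subjects per treatment instead of 36 each. The alternative text in SAP 7, followed literally, understates percentages by the factor 36/(36 + k), for example 15.0% instead of 16.7% with k = 4. The second error is smaller but harder to notice, because the result looks plausible.

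The column sizes assume 36 completers and no replacements; the dilution figures assume illustrative values of x and k. Only the further-safety percentages are at risk, and the risk comes from the text as written; it is not a demonstrated error in any table. Placement of events and the endpoint analyses are sound on this point. It should be corrected, since a stated rule gives the wrong number if it is followed.

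**What to change.** 1. Delete the first-treatment sentence from SAP 6.3, and record in SAP section 4 that this departs from protocol 7.3.
2. Put in its place: *a treated-set subject is counted under every treatment actually received*.
3. Define the percentage denominator in the further-safety tables as the treated-set subjects who received at least one dose of that treatment.
4. Amend the percentage sentence in SAP 7 to refer to that denominator. Keep its handling of missing values, so that an exposed subject with a missing value still counts.

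Leave the model specification as it is.

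The cost is wording in SAP sections 4, 6.3 and 7, and a check that the table headers use the same counts. The counts come from dosing dates and times already planned for the exposure listing (SAP 7.7). No data collection, sample size or analysis model changes.
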